8.1.2. AUC and $\frac{1}{2}$ Life Time

For serum creatinine, the 7-Day Area under the Curve (AUC), 30-Day AUC and 30 Day $\frac{1}{2}$ life time will be calculated. The formula to calculate the AUC is:

$AUC = \sum_{i=1}^M 1/2(Y_i + Y_{i-1})(d_i - d_{i-1})$ where Y_i is the serum creatinine value at Day d_i and M is the total number of measures the patient has. The 7 Day AUC will be calculated based on patients who have serum creatinine value at Day 7. The patients who will be discharged before Day 7 will be excluded from calculation. All patients are expected to have serum creatinine 30 Day post transplant. If the value is missing, the patient will be excluded from calculation.

The algorithm to determine the $\frac{1}{2}$ life time is:

1. Determine the $\frac{1}{2}$ value by $Y_{1/2} = \frac{1}{2} * Y_0$ where Y_0 is the baseline value for non-DGF patient and the value after dialysis finished for DGF patient. Denote the corresponding day d_0

2. Find the time interval between d_0 and 30 where $Y_{1/2} < Y_i$ and $Y_{1/2} > Y_{i+1}$. If no such interval, then report “NA” for that patient.

3. The approximate $\frac{1}{2}$ life time is $d_{1/2} = \frac{Y_{1/2} - Y_i}{Y_{i+1} - Y_i} (d_{i+1} - d_i) + d_i$

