11.6.2.3. Handling of Missing Data for Statistical Analysis/Efficacy Endpoints

Element	Reporting Detail
All Endpoints	
• Missing values will not be imputed.

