11.9.4. Efficacy Tables

Efficacy Tables					
No.	Population	IDS / TST ID / Example Shell	Title	Programming Notes	Deliverable
DGF					
2.01	Analysis Population	Non-Standard EFF_T3	Proportion of Subjects with DGF		IA1, IA2, SAC
2.02	Per Protocol	Non-Standard EFF_T3	Proportion of Subjects with DGF		IA2, SAC
Graft function					
2.03	Analysis Population	Non-Standard EFF_T1	Summary Statistics of Serum Creatinine		IA1, IA2, SAC
2.04	Analysis Population	Non-Standard EFF_T2	Summary of Serum Creatinine Change from Baseline		IA1, IA2, SAC
2.05	Analysis Population	Non-Standard EFF_T1	Summary Statistics of AUC of 7 Day Serum Creatinine	Only consider patients who have Day 7 serum creatinine value	IA1, IA2, SAC
2.06	Analysis Population	Non-Standard EFF_T1	Summary Statistics of AUC of 30 Day Serum Creatinine		IA1, IA2, SAC
2.07	Analysis Population	Non-Standard EFF_T1	Summary Statistics of $\frac{1}{2}$ -Life of 30 Day Serum Creatinine		IA1, IA2, SAC

Efficacy Tables					
No.	Population	IDSL / TST ID / Example Shell	Title	Programming Notes	Deliverable
2.08	All Subjects	Non-Standard EFF_T4	Proportion of Subjects with Renal Functional Graft within 7 Days after Transplant	Including primary non function;3 day functional DGF; 7 day functional DGF; 3 day intermediate graft function; 7 day intermediate graft function; 3 day immediate graft function; 7 day immediate graft function	IA1, IA2, SAC
Acute rejection risk					
2.09	All Subjects	Non-Standard EFF_T3	Proportion of Subjects with Episodes of Biopsy-Proven Acute Rejection		IA2, SAC
2.10	All Subjects	Non-Standard EFF_T2	Summary Statistics of Episodes of Biopsy-Proven Acute Rejection		IA2, SAC
PD biomarker					
2.11	All Subjects	Non-Standard EFF_T1	Summary Statistics of Serum IP-10		IA2, SAC
2.12	All Subjects	Non-Standard EFF_T2	Summary Statistics of Serum IP-10 Change from Baseline		IA2, SAC
2.13	All Subjects	Non-Standard EFF_T1	Summary Statistics of Mig		IA2, SAC
2.14	All Subjects	Non-Standard EFF_T2	Summary Statistics of Mig Change from Baseline		IA2, SAC

Efficacy Tables					
No.	Population	IDSL / TST ID / Example Shell	Title	Programming Notes	Deliverable
2.15	All Subjects	Non-Standard EFF_T1	Summary Statistics of Free IL-18		IA2, SAC
2.16	All Subjects	Non-Standard EFF_T2	Summary Statistics of Free IL-18 Change from Baseline		IA2, SAC
2.17	All Subjects	Non-Standard EFF_T1	Summary Statistics of Bound IL-18		IA2, SAC
2.18	All Subjects	Non-Standard EFF_T2	Summary Statistics of Bound IL-18 Change from Baseline		IA2, SAC

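### The creatinine half-life rule in SAP 8.1.2 mishandles a value exactly at half and does not say which crossing to use when the series re-crosses half

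*SAP*

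**What the plan says.** Section 8.1.2 gives a three-step algorithm.

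- Step 1 sets the half value to one half of a starting value, which "is the baseline value for non-DGF patient and the value after dialysis finished for DGF patient". The day of that value is the starting day.
- Step 2 tells the programmer to "Find the time interval between" the starting day and Day 30 for which the half value is strictly below the earlier creatinine and strictly above the later one. It continues "If no such interval, then report" NA for that patient.
- Step 3 interpolates linearly within the interval found and returns a day.

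The result feeds Table 2.07 in Section 11.9.4, "Summary Statistics of $\frac{1}{2}$ -Life of 30 Day Serum Creatinine", on the Analysis Population, delivered at IA1, IA2 and SAC. That row carries no programming note.

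**The concern.** The algorithm should return one day for each subject whose creatinine falls to half by Day 30, and NA for the others. As worded it fails in two situations.

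First, creatinine may land exactly on the half value. The strict test then passes over the day on which halving was observed.

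Second, creatinine may fall below half, rise above it and fall again. Step 2 speaks of one interval but its condition is met by two or more, and nothing says whether the first, the last or a sustained crossing counts. Two programmers could follow the text faithfully and report different half-lives for the same subject.

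What is at stake is the content of Table 2.07. It summarises at most 30 subjects, and fewer at IA1, so one subject wrongly set to NA or one arbitrary value can move a summary statistic.

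**Working it through.** The SAP states no numerical result here, so there is no figure to reproduce. The check applies the steps literally to constructed series.

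**Notation (Section 8.1.2).** Starting value Y0 on day d0; half value H = Y0/2; consecutive values Yi and Y(i+1) on days di and d(i+1). An interval qualifies if H < Yi and H > Y(i+1). The returned day is di + (H − Yi)/(Y(i+1) − Yi) × (d(i+1) − di).

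**Ordinary case.** 800, 700, 550, 390, 300, 250 on days 0–5, H = 400. Only (550, 390) qualifies: 2 + (400 − 550)/(390 − 550) = 2 + 150/160 = 2.938. The rule works as intended.

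**Tie, then lower.** 600, 400, 300, 200, H = 300.
- (600, 400) fails, because 300 > 400 is false.
- (400, 300) fails, because 300 > 300 is false.
- (300, 200) fails, because 300 < 300 is false.

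No interval qualifies, so the subject is NA although half was reached on a known day and creatinine kept falling. The same happens if the tie persists (800, 600, 400, 400, 400 on days 0, 1, 2, 3, 30) or first occurs at Day 30 (800, 700, 600, 500, 400 on days 0, 1, 2, 7, 30).

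**Tie, then a rise and a second fall.** 800, 600, 400, 450, 350, 300 on days 0–5, H = 400. The pair ending at the tie fails, but (450, 350) qualifies: 3 + 50/100 = 3.5. The subject is not NA, but the halving on day 2 is missed.

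**Repeat crossings.**
- 800, 600, 390, 430, 380, 420, 300, 150 on days 0, 1, 2, 3, 4, 5, 7, 30, H = 400. Three intervals qualify: 1 + 200/210 = 1.952; 3 + 30/50 = 3.6; 5 + (20/120) × 2 = 5.333.
- 800, 600, 380, 500, 450, 450, 150 on days 0, 1, 2, 3, 4, 7, 30, H = 400. Two qualify: 1 + 200/220 = 1.909 and 7 + (50/300) × 23 = 10.833. The gap is wide because the last interval runs from discharge to Day 30.

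**Fluctuation without re-crossing.** 800, 850, 600, 650, 390, 350 on days 0–5, H = 400. Only (650, 390) qualifies: 3 + 250/260 = 3.962. One answer.

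**Does another section settle it?**
- Section 11.5.1 deals with several values at one time point or within one window.
- Section 11.6.2.3 states "Missing values will not be imputed", which concerns absent values, not ties or repeat crossings.
- Section 11.4.2 settles planned versus actual time and leaves unscheduled visits out of summaries.

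None resolves either case.

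**How often would a tie matter?** The SAP gives no creatinine distribution, so any rate rests on assumptions. Assumed: starting means of 400, 600 or 800 µmol/L; exponential decline of 0.1, 0.2 or 0.35 per day towards 130; lognormal variation with CV 3%, 8% or 15%; whole-number values; days 0–7 and 30; no separate starting point for DGF subjects. Over these 27 combinations (4,000 series each), NA caused by a tie occurred in 0% to 3.0% of subjects who halved, and in under 2% in 25 of the 27. At 2%, 30 × 0.02 = 0.6 subjects; at 3%, 30 × 0.03 = 0.9.

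**How often would repeat crossings matter?** Appendix 2 schedules chemistry daily until discharge, then at D30. After the first value below half, a second crossing needs at least one later value above half and another below it. A subject discharged on the first value below half has only the D30 value left before the limit and cannot re-cross. The frequency therefore depends on length of stay, for which the SAP gives no distribution, and no rate is offered.

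**The case against.** The strongest reply is that this is a drafting matter of little consequence. The half-life is not named among the endpoints in Section 2.2; it is a derived summary of serum creatinine. It enters neither the primary analysis in Section 7 nor the predictive-probability rule in Section 3.1.1. Ties are rare, repeat crossings need inpatient values after the first fall below half, and Listing 22 shows individual creatinine values from which any half-life can be recomputed. All of this stands and limits the weight of the point. It does not make the rule correct: the text gives a wrong result on a tie and no unique result on a re-crossing. Listing 22 allows recomputation but does not show which crossing the program used; Table 3 indicates a half-life listing, yet none appears among the listings in Section 11.9.11.

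Two stronger readings are tempting and do not hold. A reader might infer that every subject who lands on half becomes NA; the series returning day 3.5 shows otherwise. A reader might also infer that any fluctuating creatinine produces several answers; the series returning only 3.962 shows that the half value itself must be re-crossed.

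It can also be said that choosing the first crossing is a preference, since under noise it leans early. That is fair. What is needed is that the SAP names one rule.

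**Conclusion.** The point holds, as a minor one. Section 8.1.2 step 2 is wrong as written for exact ties: the result is NA, or a day later than the first halving if creatinine subsequently rises above half and falls through it again. It is also ambiguous when the series re-crosses half.

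The tie should affect about 0 to 1 of at most 30 subjects, on assumed creatinine profiles that do not model the separate starting point for DGF subjects. The size of the re-crossing problem cannot be stated from the SAP, because it depends on length of stay. A reader might infer that a sizeable share of half-lives is arbitrary; the document supports no such figure.

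The effect is confined to the descriptive Table 2.07 at IA1, IA2 and SAC. Nothing here bears on the DGF primary endpoint or the go/no-go decision.

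**What to change.** Reword step 2: use the first interval with d0 ≤ di and d(i+1) ≤ 30 for which Yi > H and Y(i+1) ≤ H, where H is the half value. Report NA only if no value after d0 and up to Day 30 is at or below H. The limit to values after d0 matters for DGF subjects, whose earlier low values may fall before the starting day.

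This gives exactly one answer to every subject who reaches half. Y0 exceeds its own half, so the value just before the first one at or below H is always above H. At a tie the interpolation fraction is 1 and step 3 returns d(i+1): for 800, 700, 550, 400, 300, 250 on days 0–5 that is day 3.0. The three-crossing series returns 1.952 only.

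If the sponsor prefers a sustained crossing, state and define that instead, with an NA rule to match. Either way the lower comparison should be non-strict.

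The cost is a short rewording of step 2 before programming. No new data are needed.

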2.5. Definition of Renal Graft Function

Primary Non Function:

- Permanent lack of function of the allograft defined as an inability to discontinue dialysis from the time of transplantation. Note: The study site will decide whether patients have primary non function DGF or not and record it in data set.

3 day Functional Delayed Graft Function:

- <10% fall in SCr versus baseline per day averaged over first 3 days with OR without dialysis

7 day Functional Delayed Graft Function:

- <30% reduction in baseline SCr in first 7 days with OR without dialysis

3 day Intermediate Graft Function:

- 10- 20% fall in SCr versus baseline per day averaged over first 3 days without dialysis

7 day Intermediate Graft Function:

- 30-70% reduction in baseline Cr in first 7 days without dialysis

3 day Immediate Graft Function:

- >20% fall in SCr versus baseline per day averaged over first 3 days without dialysis

7 day Immediate Graft Function:

- >70% reduction in baseline Cr during the first 7 days without dialysis

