11.10. Appendix 10: Example Mock Shells for Data Displays

Example : EFF_F1
Protocol : 204824
Population : All Subjects

Page 1 of X

Figure X
Individual Subject Spaghetti Plot with Mean Line

[figure not shown]

NOTE: This is example only. Plot adjusted accordingly to study data.

Example : EFF_F2
Protocol : 204824
Population : All Subjects

Page 1 of X

Figure X
Individual Subject Spaghetti Plot

[figure not shown]

NOTE: This is example only. Plot adjusted accordingly to study data.

Example : EFF_F3
Protocol : 204824
Population : All Subjects

Page 1 of X

Figure X
Mean Plot of xxx

[figure not shown]

NOTE: Plot adjusted accordingly to study data

Example : EFF_F4
Protocol : 204824
Population : All Subjects

Page 1 of X

Figure X
Kaplan-Meier Curve of Graft Survival up to 12 Months post Transplant

[figure not shown]

NOTE: Plot adjusted accordingly to study data, with plot also including the other treatments groups on subsequent pages.

Example : EFF_F5
 Protocol : 204824
 Population : Safety

Page 1 of X

Figure X
 Patient Profile Plot

[figure not shown]
NOTE: Plot adjusted accordingly to study data, with plot also including the other treatments group and parameters on subsequent pages.

Example : PKPD_F1
 Protocol : 204824
 Population : All Subjects

Page 1 of X

Figure X

Scatter Plot of Free and Drug Bound IL-18 Serum Levels Versus GSK1070806 Plasma Concentration

Treatment

0.008 mg/kg HV +	0.05 mg/kg HV ✕	0.25 mg/kg HV △	1.0 mg/kg HV □	3.0 mg/kg HV *	10.0 mg/kg HV ◊
------------------	-----------------	-----------------	----------------	----------------	-----------------

Note: IL-18 Serum values defined as BLQ, are imputed as half of LLQ.

Note: Analysis numeric results in std units (NQ values not imputed with 0) are considered as Plasma Concentration values.

Note: Free IL-18 plot is not presented as majority of data is BLQ.

Note: Doses = 0.008, 0.05, 0.25, 1.0, 3.0 & 10 mg/kg HV

Example : EFF_T1
 Protocol : 204824
 Population : All Subjects

Page 1 of X

Table X
 Summary Statistics of XXX (unit)

Summary: Absolute

Treatment	N	Visit	Planned Relevant Time	n	Mean	S.D	Median	Min	Max
GSK1070806 3 mg/kg	xx	xx	x		XXX.X	XX.XX	XXX.X	XXX	XXX
	xx		x		XXX.X	XX.XX	XXX.X	XXX	XXX
	xx	xx	x		XXX.X	XX.XX	XXX.X	XXX	XXX
	xx		x		XXX.X	XX.XX	XXX.X	XXX	XXX

Example : EFF_T2
 Protocol : 204824
 Population : All Subjects

Page 1 of X

Table X
 Summary Statistics of XXX (unit)

Summary: Change from Baseline

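### Table 2.07 summarises creatinine half-life only in subjects who halved by Day 30, and leans towards faster recovery by an amount the SAP cannot show

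*SAP*

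**What the plan says.** **The algorithm.** SAP Section 8.1.2 sets a reference value: "Y_0 is the baseline value for non-DGF patient and the value after dialysis finished for DGF patient". The day of that value is d_0. Step 2 is "Find the time interval between d_0 and 30 where" creatinine crosses half of the reference value. Where there is no crossing: "If no such interval, then report “NA” for that patient".

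**Missing data.** Section 11.6.2.3, for all efficacy endpoints: "Missing values will not be imputed".

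**The display.** Section 11.9.4 sends the result to Table 2.07 (its title ends "Life of 30 Day Serum Creatinine"), on the Analysis Population, at IA1, IA2 and SAC, using shell EFF_T1. In Appendix 10 that shell has columns for N, visit, "Planned Relevant Time", n, mean, SD, median, minimum and maximum. It has no row for subjects who did not halve, no proportion halved and no time-to-event estimate.

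**Individual data.** Table 3 marks an individual listing for the half-life, but Listings 22 to 24 in Section 11.9.11 cover creatinine and its two AUCs only.

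**The concern.** For a subject followed to Day 30, NA is information: no halving was seen by then. Dropping these subjects makes the summary conditional on the event it is meant to time.

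Some of the poorest grafts leave by another route. Section 2.5 defines primary non function as "Permanent lack of function of the allograft defined as an inability to discontinue dialysis from the time of transplantation". Such a subject, or anyone else still on dialysis at Day 30, has no post-dialysis value, so no Y_0, no d_0 and no half-life.

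At the interim deliveries NA takes on another meaning. IA2 is triggered when the last subject reaches Day 7, so recent subjects can have well under 30 days of data. One who has already halved gets a number; one who has not gets NA, exactly like a subject followed to Day 30 without halving.

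At stake is a half-life table that reads more favourably than the cohort it describes, in deliveries used for internal decisions.

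**Working it through.** The SAP states no figure for the half-life, so there is none to reproduce. Its only design figures, go probabilities of 0.139 and 0.69 in the Synopsis, recompute as 0.1389 and 0.6895. They depend on DGF counts alone and are not inputs here.

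**Inputs from the SAP:** search window d_0 to Day 30; NA if no crossing; no imputation; summary over subjects with a value.

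**Assumed:** the distribution of time to halving, because the SAP gives none. Three forms were tried.

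**1. Exponential times, full 30-day window.** With true median m, the share halved is F = 1 − 2^(−30/m). The median among halvers, t, solves 1 − 2^(−t/m) = F/2, so t = −m·log2(1 − F/2).

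| True median m (days) | F | Share NA | Median Table 2.07 would report |
|---|---|---|---|
| 5 | 0.984 | 2% | −5·log2(0.508) = 4.9 |
| 10 | 0.875 | 13% | −10·log2(0.5625) = 8.3 |
| 20 | 0.646 | 35% | −20·log2(0.677) = 11.3 |
| 30 | 0.500 | 50% | −30·log2(0.750) = 12.5 |
| 60 | 0.293 | 71% | −60·log2(0.854) = 13.7 |

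With complete follow-up and non-halvers kept as not halved by Day 30, the Kaplan-Meier median is 5, 10, 20 and 30 in the first four rows and not reached in the last.

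**2. Other shapes.** Lognormal times with sigma 0.6 and true medians of 5, 10, 20, 30 and 40 days give reported medians of 5.0, 9.8, 16.5, 20.0 and 21.9. With sigma 1.0 they are 4.8, 8.4, 12.8, 15.3 and 16.8. The tighter the distribution, the smaller the distortion at moderate medians.

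**3. Poorer recovery as more never-halving grafts.** Grafts that recover have lognormal times with median 4 days and sigma 0.5; a share q never halves by Day 30. The retained median solves (1 − q)·F(t) = 0.5.

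| q | SAP rule: mean / median | Median with non-halvers kept |
|---|---|---|
| 0 | 4.5 / 4.0 | 4.0 |
| 0.20 | 4.5 / 4.0 | 4.7 |
| 0.35 | 4.5 / 4.0 | 5.8 |
| 0.50 | 4.5 / 4.0 | not reached |
| 0.70 | 4.5 / 4.0 | not reached |

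Here the reported mean and median do not move; only n falls.

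**Sampling.** Appendix 2 schedules chemistry daily to discharge, at discharge, then at Day 30. A crossing after discharge is therefore interpolated linearly over a wide gap. In simulated declining curves with discharge on Day 7, true medians of 4.8, 9.5, 19.9 and 39.4 days were reported as 4.6, 12.3, 20.6 and 25.0, with 5%, 7%, 26% and 68% NA. At 19.9 days the true median among those reported was 16.4, so interpolation offset the selection.

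**The case against.** Several points on the other side stand.

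- **Sensitivity.** A reader might infer that the table hardly changes however slow recovery becomes. The SAP does not support that in general. If all grafts slow down but most still halve within the window, the table responds: a true median going from 5 to 10 days moves the reported one from 4.9 to 8.3 (exponential). Near-insensitivity needs either slowing that shows up as more non-halvers or, under the exponential model, true medians of about 20 days or more.
- **Who is summarised.** A reader might infer that only fast-recovering grafts enter. For DGF subjects the reference is reset to the post-dialysis value, so a late-recovering graft can still have a half-life. A graft starting from a low reference can be NA despite good function.
- **Visibility.** The shell shows both N and n, so the number without a value can be derived.
- **Role.** Half-life is not an endpoint in Section 2.2. Poor grafts remain visible in Tables 2.03, 2.04, 2.08 and 2.24, Figures 2.01 and 2.04, and Listing 33. It would be wrong to say that graft function cannot be assessed.
- **Interims.** Only subjects who have not yet halved are affected, not everyone with under 30 days of data.
- **Remedy.** A Kaplan-Meier analysis needs one origin. Y_0 and d_0 differ by DGF status and do not exist for continuing dialysis.

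These limit the reach of the point. They do not answer it: N minus n does not separate no halving by Day 30, no reference value, a missing sample and short follow-up, and the statistics remain conditional on halving.

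**Conclusion.** The point holds as a defect in a stated rule, not an omitted detail. Table 2.07 describes subjects who halved by Day 30, is not labelled as such, and is biased towards faster recovery for the cohort as a whole.

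The size rests on assumptions. It is slight if nearly all subjects halve well inside 30 days. Under exponential times a true median of 20 days is reported as about 11.3 and one of 60 days as about 13.7; under tighter distributions the shortfall is smaller, and sparse sampling after discharge can offset it. Where worse recovery means only more non-halving grafts, the mean and median carry no signal of it.

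The consequence is limited to one supplementary descriptive display in a single-arm pilot of at most 30 subjects. The primary DGF analysis and the sequential Go/No Go rule do not use it. The change should be made because it is cheap and the table goes to both interim deliveries.

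**What to change.** In Section 8.1.2 and Table 2.07:

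1. State one time origin and one definition of halving for all subjects, including those with continuing dialysis. This must be settled first.
2. Report the number and proportion halved by Day 30, with the Analysis Population as denominator.
3. Replace the mean and SD among halvers with a Kaplan-Meier median, shown as not reached where that is so.
4. Count subjects on dialysis throughout, and those who die or lose the graft before halving, as not halved through Day 30. Censor all other non-halvers at Day 30, or at last creatinine if earlier; this also deals with short follow-up at IA1 and IA2.
5. If halvers-only statistics are kept, label them as conditional on halving by Day 30.
6. Add the half-life listing that Table 3 already promises, with the reason for each NA.

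The cost is SAP wording, a revised table and one listing. Kaplan-Meier is already planned for graft survival. The downsides are that the median may not be reached and that agreeing the time origin takes some work.

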8.2. Safety Analyses

8.2.1. Overview of Planned Analyses

The safety analyses will be based on the “All Subjects” population, unless otherwise specified.

Table 4 provides an overview of the planned analyses with further details of data displays being presented in Appendix 11.10: List of Data Displays.

Table 4 Overview of Planned Safety Analyses

Endpoint / Parameter/ Display Type	Absolute				Change from Baseline			
	Summary		Individual		Summary		Individual	
	T	F	F	L	T	F	F	L
Adverse Events¹								
All	Y			Y				
Drug-Related	Y			Y				
Serious	Y			Y				
Leading to Withdrawal	Y			Y				
Laboratory Assessments								
Haematology	Y			Y				
Clinical Chemistry ² :	Y			Y				
Routine Urinalysis:				Y				
ECG								
ECG Findings	Y			Y				
ECG Measures	Y			Y	Y	Y		Y
Vital Signs								
Vital Signs	Y			Y		Y	Y	
Immunogenicity								
Frequency of Anti-drug antibodies				Y				
ADA titers				Y				

NOTES :

- T = Table, F = Figure, L = Listing, Y = Yes display generated..
- Summary represents any summaries (i.e. descriptive statistics) of the observed raw data.
- Individual represents any displays of individual subject observed raw data.

1. Listings will include subject’s numbers for individual AE’s & AE system organ classes, preferred terms and verbatim text.

Endpoint / Parameter/ Display Type	Absolute				Change from Baseline			
	Summary		Individual		Summary		Individual	
	T	F	F	L	T	F	F	L
2. Chemistry (includes LFTs and lipids) & haematology/coag summaries will include both changes from baseline & emergent results by PCI criteria. Listings for subjects with abnormalities of PCI will be prepared.								

